6.4. VITAL SIGNS

Changes from baseline will be calculated for each vital sign parameter (systolic and diastolic blood pressure, pulse, weight and temperature) for each scheduled visit. Change

from baseline for systolic and diastolic blood pressure will be calculated irrespective of whether the arm used for the blood pressure assessment is the same at both visits.

6.5. ECGs

Changes from baseline will be calculated for each ECG parameter (heart rate, QRS duration, PR interval QT interval and QTcF interval) for each scheduled visit.

6.6. PHYSICAL EXAMINATION

Any physical examination abnormality considered clinically significant in the medical and scientific judgment of the Investigator (i.e., not related to progression of underlying disease), will be reported as an AE.

6.7. EYE EXAMINATIONS

Eye examination data will be performed during the study by an appropriately qualified professional. Any abnormality considered clinically significant, will be reported as an AE.

To allow for scheduling of the eye examinations the REN001-201 Week 24 (Month 6) assessment can occur up to 14 days after the visit. Hence, this examination could occur after the start of administration of mavodelpar in REN001-202; this period is not considered sufficient time to have an impact on eye examination results. Therefore, for those mtDNA-PMM subjects who received placebo in REN001-201, enrolled in REN001-202 at REN001-201 Exit, enrol from study REN001-101 or for nDNA-PMM subjects this record will still be considered the baseline record relative to the start of mavodelpar provided it occurs within 14 days of the first dose of mavodelpar.

Baseline eye examinations will not be required for REN001-201 Exit subjects if the screening visit is within 6 months of the last REN001-201 examination.

Best corrected visual acuity (BCVA) can be assessed using the LogMAR scale, ETDRS letters or Snellen line. All results will be converted to the LogMAR scale before calculating changes from baseline at each visit for left and right eye BCVA (Roy 2003).

Where the Snellen scale has data recorded as x/y the MAR value is calculated by dividing y by x and then the LogMAR is the base 10 logarithm of the MAR value [i.e., $\text{LogMAR} = \log_{10}(\text{MAR})$]. Hence, higher scores indicate worse BCVA and increases from baseline indicate deterioration.

A change of 0.02 in LogMAR is equivalent to 1 letter. Hence, a Snellen scores with ‘-z’ or ‘+z’ indicating z letters fewer, or z letters more, respectively, will require an adjustment to the LogMAR score; 0.02 will be added or subtracted, respectively, for each letter (z).

e.g.,

$$20/15-1: \text{LogMAR} = \text{Log}_{10}(15 \text{ divided by } 20) + 0.02 = -0.105$$

$$20/15+1: \text{LogMAR} = \text{Log}_{10}(15 \text{ divided by } 20) - 0.02 = -0.145$$

If the Snellen scale is not reported in x/y format or x/y±z format, then the conversion to logMAR will not be done.

A change of 0.3 LogMAR (equivalent to 15 letters or 3-line change) is considered meaningful.

Refraction error based on spherical equivalent will be derived for each eye using the following formula:

$$\text{Spherical Equivalent (diopters)} = \text{cylinder (diopters)}/2 + \text{sphere (diopters)}$$

Changes from baseline at each visit will be calculated.

Cataract are classified and graded against the Lens Opacity Classification System III (LOCS III) for nuclear opalescence, nuclear colour, cortical and posterior subcapsular cataracts. Changes from baseline will be calculated. Higher scores equate to a deterioration in cataracts. The largest increase from baseline (or smallest decrease if both eyes show a reduction from baseline) across the eyes will be identified at each visit.

6.8. COVID-19 EXPOSURE AND VACCINATION DATA

Information on whether a subject has had exposure to COVID-19 or received a COVID-19 vaccination is collected on a specific eCRF page. Further details of COVID-19 events will be recorded in either medical history or on an adverse event page, depending on the timing; and further details of COVID-19 vaccinations will be recorded on the concomitant page.

7. ANALYSIS SETS AND PROTOCOL DEVIATIONS

7.1. SCREENED ANALYSIS SET

The screened analysis set will include all subjects who signed the REN001-202 informed consent form and are screened for participation in REN001-202.

7.2. SAFETY ANALYSIS SETS

There will be a separate safety set for each of the approaches for summarizing the data.

- from the start of REN001-202 – will include all REN001-202 subjects who signed the REN001-202 informed consent form, completed screening and received at least one dose of mavodelpar study medication in REN001-202.
- From the start of REN001-201 – will include all subjects who signed the REN001-201 informed consent form, completed screening and received at least one dose of study medication in REN001-201.
- from the start of REN001 treatment – will include all subjects who signed the informed consent form (REN001-201 form for mavodelpar REN001-201 subjects and REN001-202 form for REN001-201 placebo subjects), completed screening and received at least one dose of mavodelpar study medication in either REN001-201 (mavodelpar subjects in REN001-201) or REN001-202 (placebo subjects in REN001-201).

The ‘from the start of REN001-201’ safety analysis set summaries will be based on the actual treatment received. The safety analysis sets will be used for all baseline and safety analyses.

A listing safety analysis set will be used for listings. This will include all subjects who signed the informed consent form and received at least one dose of study medication in either REN001-201 or REN001-202.

7.3. FULL ANALYSIS SETS

There will be a separate full analysis set (FAS) from the start of REN001-202 and from the start of REN001-201 approaches for summarizing the data.

- from the start of REN001-202 – will include all REN001-202 subjects who signed the REN001-202 informed consent form, completed screening, received at least one dose of mavodelpar study medication in REN001-202 and have not been subsequently discontinued from the study for failing eligibility criteria.
- from the start of REN001-201 – will include all subjects who signed the REN001-201 informed consent form, completed screening, received at least one dose of

study medication in REN001-201 and have not been subsequently discontinued from the study for failing eligibility criteria.

Subjects will be analysed according to the treatment they were assigned at REN001-201 randomization for the ‘from the start of REN001-201’ analyses. The FAS will be the primary analysis set for efficacy.

7.4. PHARMACOKINETIC ANALYSIS SET

The PK set will include all subjects in the safety set who receive mavodelpar in REN001-202 and have at least one evaluable (i.e., not impacted by any important protocol deviations or other events) PK measurement (even if below the limit of quantification) in REN001-202.

Note, intense PK sampling will not be performed on all subjects if it is deemed that sufficient data (i.e., full sampling in approximately 20 -30 subjects) has been collected.

7.5. DXA SCAN ANALYSIS SET

The DXA scan set will include all subjects in the safety set who have a valid REN001-202 Month 24 or Month 48 (or Early Termination) DXA scan (i.e., with parameter measurements). The DXA scan set will be used for analysis of the DXA data.

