8 STATISTICAL METHODS

A formal Statistical Analysis Plan (SAP) will be finalized prior to locking the study database. The full details of data presentations and analyses will be provided in the SAP. Additional statistical analyses other than those described in this section may be performed if deemed appropriate and included in the SAP. Any deviations from the final SAP will be discussed in the final Clinical Study Report.

As this study is the open-label extension study to STRIDE, the two studies will be reported together. In addition to data being presented from the start of REN001-202, the data will also be presented from the start of STRIDE and from the start of REN001 treatment for mtDNA-PMM subjects. This will allow the assessment of long-term safety and efficacy from the start of dosing in STRIDE for those who received REN001 in STRIDE, as well as from the start of REN001 in this study.

Presentations from the start of REN001-202 will include all mtDNA-PMM subjects who receive at least one dose of REN001 in this study. The presentations will be split by the various options for entering the study, and by the STRIDE treatment group (REN001, Placebo) for those subjects who participated in STRIDE. nDNA-PMM subjects will also be summarized from the start of REN001-202.

Presentations from the start of STRIDE will include all mtDNA-PMM subjects who receive at least one dose of study drug in the STRIDE study. These will be split by the STRIDE treatment groups (REN001, Placebo). For those subjects who are enrolled into this study after exiting STRIDE only the data collected in STRIDE will be summarized in these presentations.

Presentations from the start of REN001 treatment will summarize the data emergent during treatment with REN001. These summaries will include all mtDNA-PMM subjects who receive REN001 in STRIDE and/or this study.

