8.1.3 Analysis Populations

Separate safety and full analysis sets will be identified for the different approaches to summarizing the data (start of REN001-202, start of STRIDE or start of REN001 treatment). Precise details of the analysis sets are dependent on the approach and will be defined further in the SAP, but the general definitions are:

Screened Set	All subjects who sign the informed consent form.
Safety Set/Full Analysis Set (FAS)	All subjects who receive at least one dose of study treatment .
PK Set	All subjects in the FAS who have at least 1 evaluable post-dose PK measurement (even if this is <Level of

	Quantification (LOQ) in this study.
Scan Set	All subjects in the FAS who have evaluable post-baseline DXA endpoint data.

Safety and efficacy analyses will be based upon the Safety and FAS analysis sets, respectively.

After all the data have been verified/coded/entered into the database, a review will be performed. The purpose of this review will be to define the analysis populations. The review will also check the quality of the data, identify outliers, and make decisions on how to deal with any data issues (e.g., missing values, withdrawals, protocol deviations). After the pre-analysis review, resolution of all issues and documentation of all decisions, the database will be locked.

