12.3. DUAL ENERGY X-RAY ABSORPTIOMETRY (DXA) SCAN

Summaries of DXA data will only be presented from the start of REN001-202 and from the start of REN001 treatment.

Observed, change from baseline and percent change from baseline values for the DXA endpoints will be summarized for the DXA set. The summary will be presented overall within the group and by sex and menopausal status (i.e., men, pre-menopausal women and post-menopausal women).

A box and whisker plot will be presented for each of the parameters measuring the total spine and the 2 hip regions (total and femoral neck), for the DXA set. The whiskers will display the 5th and 95th percentiles and outliers will be identified on the plot with subject ID. The plot will present the visits alongside one another for each group. The plot will be repeated by sex and menopausal status.

For the DXA set, the study day of the follow-up DXA scans (Months 6, 30 and 54 relative to the start of REN001-201) will be summarized using descriptive statistics.

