13. INTERIM ANALYSES

An interim synoptic CSR will be prepared for this study to be included in the regulatory submission package. The data cut will be the date of the last subject last visit in REN001-201 and the data will be extracted from the database after REN001-201 database has been locked. This CSR will include all REN001-202 data up to the data cut date and best efforts will be made to clean data up to this data cut date.

There will be a reduced set of safety outputs generated after submission for the 120-day safety update which is required as part of the submission package. The final CSR will occur after all subjects have had the ability to complete REN001-202, the data has been cleaned and the database locked.

An independently chaired Safety Review Committee (SRC) will review safety data at specified intervals for the duration of the study. The structure, function and operation of the SRC is detailed in the REN001-202 SRC charter. The SRC review of safety data will be limited to data from REN001-202 and will not be combined with REN001-201 data.

**14. CHANGES FROM PLANNED ANALYSES SPECIFIED
IN THE PROTOCOL**

None.

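### From the start of REN001, the Month 6 bone summary is limited to subjects who have a later REN001-202 DXA scan, which is narrower than the protocol's general Scan Set and not declared as a change

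*SAP*

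**What the plan says.** SAP 7.5 opens: "The DXA scan set will include all subjects in the safety set who have a valid REN001-202 Month 24 or Month 48". The sentence continues so that an Early Termination scan also qualifies; the full condition is "who have a valid REN001-202 Month 24 or Month 48 (or Early Termination) DXA scan". It does not say which of the three safety sets in SAP 7.2 is meant. It gives the set one role: "The DXA scan set will be used for analysis of the DXA data".

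SAP 12.3 names two presentations: "Summaries of DXA data will only be presented from the start of REN001-202 and from the start of REN001 treatment". The same section counts Month 6 among the follow-up scans, with Months 30 and 54.

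Protocol 8.1.3 defines the Scan Set as "All subjects in the FAS who have evaluable post-baseline DXA endpoint data". It introduces its definitions with: "Precise details of the analysis sets are dependent on the approach and will be defined further in the SAP, but the general definitions are". For presentations from the start of REN001 treatment, Protocol Section 8 says: "These summaries will include all mtDNA-PMM subjects who receive REN001 in STRIDE and/or this study".

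SAP Section 14 lists no change from the protocol's planned analyses.

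**The concern.** A subject randomised to mavodelpar in the STRIDE DXA sub-study can have a valid pre-dose scan at screening and a valid on-drug scan at Week 24. That pair gives a complete Month 6 change in bone mineral density from the start of REN001. SAP 7.5 discards it from the summaries unless the subject is scanned again in REN001-202.

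The later scan depends on entering the extension, staying on drug, agreeing to an optional procedure and having a usable image. Several of these are plausibly related to tolerability or health. The Month 6 summary would then describe those who continued rather than those who were exposed. Bone is a safety question that the protocol raises itself (Section 1.4.2.6), and evaluating bone health is a stated exploratory objective (Section 2.4).

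**Working it through.** The plan states no figure to reproduce here. The check compares the two definitions, subject type by subject type, and then illustrates the size.

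**Step 1. Is the Week 24 scan post-baseline?**
- From the start of REN001-202: no. Baseline is the last assessment before REN001-202 dosing (Protocol 8.2.3, SAP 8.6), and Protocol 4.4 takes the STRIDE Week 24 scan as this study's baseline.
- From the start of REN001, for subjects given mavodelpar in STRIDE: yes. Both documents set baseline before STRIDE dosing (Protocol 8.2.3, SAP 8.6). For DXA that is the screening scan (SAP 6.3, SAP Appendix 2).

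**Step 2. Who belongs in the from-start-of-REN001 population?** Subjects dosed with mavodelpar in REN001-201 qualify whether or not they enter REN001-202 (Protocol Section 8, SAP 7.2).

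**Step 3. Membership for STRIDE mavodelpar subjects with a valid screening scan and a valid Week 24 or STRIDE early-termination scan.**

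| Subject type | Protocol general definition | SAP 7.5 |
|---|---|---|
| Completed STRIDE, never entered REN001-202 | in | out |
| Stopped STRIDE treatment after at least 20 weeks and was scanned (SAP Appendix 2, note 21); cannot enter REN001-202, because entry from STRIDE requires completed treatment (Protocol 4.1.1) | in | out |
| Left REN001-202 before Month 24 with under 20 weeks of dosing after the baseline scan, so no withdrawal scan (Protocol 6.9) | in | out |
| Stayed, but declined the optional scan (Protocol 4.4) or had an invalid one | in | out |
| At an interim cut, no Month 24 or Early Termination scan yet | in | out |
| Has a valid REN001-202 Month 24, Month 48 or Early Termination scan | in | in |

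Subjects who exit STRIDE and return later (Group 4a) count as two separate subjects from the start of REN001 (SAP 8.2). Their first participation has no REN001-202 scan of its own, and the SAP does not say how the DXA set treats it.

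**Step 4. Can another summary recover these changes?** No. SAP 12.3 plans no DXA summary from the start of REN001-201. Placebo subjects do not fill the gap either: from the start of REN001 their baseline is the REN001-202 one, and their next scheduled scan is at REN001-202 Month 24.

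**Step 5. Illustrative size.** Let f be the share of scanned STRIDE mavodelpar subjects without a later valid scan. The documents do not give f, so the values below are assumptions. Month 6 n falls to (1 − f)n. With an unchanged standard deviation, the standard error of the mean change is multiplied by 1/√(1 − f).

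| f (assumed) | n retained | Standard error factor |
|---|---|---|
| 0.10 | 90% | 1/√0.90 = 1.05 |
| 0.25 | 75% | 1/√0.75 = 1.15 |
| 0.40 | 60% | 1/√0.60 = 1.29 |

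The factor covers precision only. Any bias from the selection comes on top, and the documents do not allow it to be quantified.

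**The case against.** **The protocol leaves the detail to the SAP.** It calls its definitions general, so a reader who infers that the SAP simply breaches the protocol goes too far. That stands. But the protocol also says that the detail depends on the approach, and the SAP applies one rule to both.

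**The endpoint is change to end of treatment.** The Scan Set wording refers to endpoint data, and the DXA endpoint is change from baseline to end of treatment (Protocol 3.2.4, SAP 3.2.4). For a subject still on drug, Month 6 is not the end of treatment, so requiring a later scan can be read as applying the endpoint. This does not cover subjects treated with mavodelpar only in STRIDE, for whom the Week 24 or early-termination scan is the end-of-treatment scan. Nor does it fit SAP 12.3, which treats Month 6 as a follow-up.

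**Nothing is deleted.** Data for anyone in a safety set are listed (SAP 8.2). Bone markers (SAP 12.2) and fractures, as events of special interest (SAP 6.1 and 12.1), are summarised on the safety sets. That also stands: the loss is confined to DXA summaries and plots.

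**The interim report.** SAP Section 13 sets the cut: "The data cut will be the date of the last subject last visit in REN001-201". Month 24 is Day 672 ± 21, so Day 651 at the earliest (672 − 21). A reader might infer that most Month 6 data would be missing from the interim report. The documents do not support this: they do not list DXA among the interim outputs, they give no counts, and subjects with an Early Termination scan stay in the set.

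**Conclusion.** The point holds for one of the two DXA presentations. From the start of REN001, SAP 7.5 makes the Month 6 bone result conditional on a scan taken later in REN001-202. It leaves valid pre-dose to on-drug changes out of the summaries, in a way that is plausibly informative. The rule is narrower than the protocol's general definition, and Section 14 does not declare it. From the start of REN001-202 the rule is appropriate.

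The number affected is unknown. The range of 10% to 40% fewer subjects at Month 6, with a standard error 1.05 to 1.29 times as large, rests on the assumed share without a later scan and on an unchanged standard deviation. The endpoint is exploratory, the scans are optional, and no test or sample size depends on them. The change is worth making, but it does not touch the primary safety endpoints.

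**What to change.** Define the DXA set separately for each presentation in SAP 7.5, naming the safety set that applies:

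- **From the start of REN001-202:** keep the present rule.
- **From the start of REN001 treatment:** include safety-set subjects with a valid baseline scan for that presentation and at least one valid later scan. For subjects given mavodelpar in STRIDE, count the REN001-201 Week 24 or early-termination scan. State how the first participation of Group 4a is handled.

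State whether DXA is summarised at the interim. If the sponsor prefers the present restriction, declare and justify it in Section 14.

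The cost is SAP wording and the matching table and figure shells; the scans are already part of the two studies. The drawback is small: n will differ by visit and by presentation, so each table should show n per visit.

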7.6. PROTOCOL DEVIATIONS

Protocol deviations may be identified by site staff, study monitors and medical monitor reviewers. They may also be identified through programmable checks of the data. Site specific protocol deviations will be provided separately from the subject specific protocol deviations.

Protocol deviations will be reviewed on an ongoing basis and categorized by Reneo Pharma Ltd. as either minor or major prior to database lock. Minor deviations are those that do not produce or have the potential to cause harm, do not impact the integrity of the trial, and cannot be avoided due to the subject’s schedule or natural events. In contrast, major deviations are events that may have a significant impact on subject’s rights or safety, or the integrity of the clinical study data. No subjects will be excluded from the safety set due to protocol deviations.

Only protocol deviations from REN001-202 will be listed; the REN001-201 protocol deviations will be listed in the REN001-201 CSR. The number of subjects reporting major deviations in either study will be summarized overall and by deviation category.

8. GENERAL ASPECTS FOR STATISTICAL ANALYSIS

8.1. HYPOTHESIS TESTING

No formal statistical testing is planned.

8.2. GENERAL METHODS

Continuous variables will be summarized using the number of non-missing observations (n), mean, SD, median, minimum, and maximum. Categorical variables will be summarized using counts and percentages.

Unless otherwise specified, the estimated mean and median for a set of values should be displayed to 1 more decimal place than the original values, and SD should be displayed to 2 more decimal places than the original values. The minimum and maximum should be displayed to the same number of decimal places as the original values. Deviations from this convention may arise to take account of the relevance of the precision (e.g., the distance walked in the 12MWT is reported to the nearest cm, but there is no relevance in presenting the mean to the nearest mm). These deviations from convention will be documented in the relevant analysis sections below.

Percentages will be displayed with 1 decimal place; except percentages will not be presented when the count is zero and 100% will be presented as an integer. Unless stated otherwise, percentages of subjects will be based on the number of subjects with non-missing data in the analysis set used for the presentation.

Unless stated otherwise, an on-treatment measurement will be any measurement collected (including scheduled and unscheduled visits) up to the date of last dose plus one day. Drug interruptions will not be considered, i.e., data will not be excluded during a drug interruption if the subject resumes study treatment; this includes the follow-up period for subjects who enrol in REN001-202 at the REN001-201 FU.

In by-visit summary tables, the baseline will be summarized using all available data, but also for each visit using only the baseline data from subjects with available data at the visit; hence the mean change from baseline will equal the mean observed visit value – mean baseline value.

Throughout this document ‘change from baseline’ refers to the actual change from baseline (i.e., observed visit value – baseline value). The baseline definitions are detailed in [Section 8.6](#).

There will be 3 approaches to summarising the data and, unless stated otherwise, all presentations will be presented for each approach. [Figure 1](#) in [Section 2](#) shows the different pathway options a subject can enter REN001-202 and the 5 distinct reporting groups these

subjects represent. These 5 reporting groups are referenced in square brackets alongside the descriptions below. The summaries are:

- From the start of REN001-202 Summaries will be presented by mutation group (REN001 100 mg mtDNA-PMM [Groups 1 to 4] and REN001 100 mg nDNA-PMM [Group 5]). The mtDNA-PMM group will also be split by:
 - Placebo > REN001 100 mg [Group 1] – subjects who received placebo in REN001-201 and enrolled at REN001-201 W24, FU or after exit.
 - REN001 100 mg > REN001 100 mg [Group 2] – subjects who received mavodelpar in REN001-201 and enrolled at REN001-201 W24 visit.
 - REN001 100 mg >FU> REN001 100 mg [Group 3] – subjects who received mavodelpar in REN001-201 and enrolled at REN001-201 FU visit.
 - REN001 100 mg >Exit> REN001 100 mg [Groups 4a and 4b] – subjects who received mavodelpar in REN001-201 and enrolled after exiting REN001-201 or subjects who took part in REN001-101 study.

Summaries will extend out to Month 48, where applicable.

- From the start of REN001-201 which will be split by REN001-201 treatment group (REN001 100 mg [Groups 2, 3 and 4a] and placebo [Group 1]). Subjects who enrol in REN001-202 at REN001-201 Exit will only have their REN001-201 data included in these summaries. Baseline summary tables (disposition, demography, baseline characteristics, medical history and prior medications) will also include an overall summary.

Summaries will extend out to Month 54, where applicable, for all subjects who complete both studies.

- From the start of REN001 treatment [Groups 1, 2, 3 and 4]. Subjects who enrol in REN001-202 at REN001-201 Exit and receive mavodelpar in REN001-201 [Group 4a] will be counted as 2 separate subjects. Summaries will be presented over all subjects (REN001 100 mg).

Summaries will extend out to Month 54, where applicable, for subjects who receive mavodelpar in REN001-201 and enrol in REN001-202 at REN001-201 W24 or FU; for all other subjects summaries will extend to Month 48.

In addition, for summaries from the start of REN001 there is only Week 2 (Month 0.5), Week 18 (Month 4.5), Month 1 (Month 7) and Month 3 (Month 9) for subjects who receive mavodelpar in REN001-201 and therefore this visit will not be included in the by visit summaries. Refer to [Section 3.8](#) for diagram of visit assignment.

All data for subjects included in at least one safety analysis set will be listed. For screen failures, only REN001-202 screen failure subjects will have data listed, and this will be limited to disposition (including reason for screen failure), demographics and protocol deviations.

Data listings will be ordered by REN001-201 treatment group (REN001 100 mg, Placebo, Not Applicable), REN001-202 enrolment (REN001-201 W24, REN001-201 FU, REN001-201 Exit, REN001-101 or nDNA-PMM subjects) and subject. For those subjects who do not enter REN001-202 their REN001-202 enrolment will be identified as ‘Not Applicable’. Study data from both REN001-201 and REN001-202 will be listed unless stated otherwise, and the listing will indicate the study source of the data. The visit listed will be the original visit for the associated study. A subject’s mutational genotype (m.3243A>G, m.8344A>G, mt deletion or Other) will be identified on the listings for mtDNA-PMM subjects. In addition to dates, data listings will present study days relative to:

- Start of REN001-201 dosing (if applicable)
- Start of REN001-202 dosing (if applicable)

Study day will be derived as per SDTM guidelines i.e., study day is derived as (assessment date – first day of dosing +1) after the start of dosing and as (assessment date – first day of dosing) before the start of dosing.

Changes from baseline will be included in listings. More than one change from baseline will be presented if more than one baseline is used (Refer to [Section 8.6](#)). All statistical analyses will be performed using SAS® (Version 9.4 or higher, SAS Institute Inc., Cary, NC, USA).

